4.7 Interim Analysis for Efficacy

There are no planned interim analyses of the endpoints. Interim reports pertaining to the progress of this study will be submitted to the US FDA for review annually until study completion.

5 Safety Analysis Strategy

5.1 Safety Endpoints

The safety endpoints are:

Primary Safety (6 months)

- Cumulative rate of secondary surgical interventions (SSIs) related to the optical properties of the IOL
- Binocular Distance Contrast Sensitivity
 - Photopic without glare (3, 6, 12, 18 cycles per degree)
 - Photopic with glare (3, 6, 12, 18 cycles per degree)
 - Mesopic without glare (1.5, 3, 6, 12 cycles per degree)
 - Mesopic with glare (1.5, 3, 6, 12 cycles per degree)

Secondary Safety (6 months)

- Rates of severe and most bothersome (separately) visual disturbances as reported by the subjects using a questionnaire (QUVID)

Third Safety (6 months)

- Cumulative and persistent rates of Adverse Events in first operative eyes

Other Safety

- Rates of all visual disturbances as reported by the subjects using the QUVID questionnaire at 6 months
- IOP
- Slit lamp observations
- Dilated fundus observations
- Ability to evaluate the fundus at 1 month
- Rates of ocular adverse events, including SSIs related to the optical properties for either eye
- Adverse events
- Device deficiencies
- IOL observations

- IOL position change
- Subjective PCO
- Posterior Capsulotomies
- Surgical Problems
- [REDACTED]

5.2 Safety Hypotheses

Rates of cumulative and persistent adverse events listed in IS EN ISO 11979-7:2014 will be compared to historical control Safety and Performance Endpoint (SPE) rates. The focus of the safety analysis will be a comprehensive descriptive assessment of safety endpoints listed in Section 5.1.

5.3 Statistical Methods for Safety Analyses

Except otherwise stated, the analysis set for all safety analyses is the safety analysis set as defined in Section 2.2. Baseline will be defined as the last measurement prior to exposure to investigational product, except otherwise stated.

5.3.1 Secondary Surgical Interventions

Descriptive summaries (count, rate and 95% (two-sided) exact confidence interval) of secondary surgical interventions will be presented for each IOL group and the difference between the groups, separately for first operative eyes and all eyes in each of the following categories:

- 1) Related to IOL - due to optical properties
- 2) Related to IOL - not due to optical properties
- 3) Unrelated to IOL
- 4) Overall

A listing of all SSIs will also be presented.

The following SAS pseudo code will be used.

```
proc freq data=SSI;
  tables LENS_MODEL*SSI / alpha=0.05;
  exact riskdiff;
  run;
```

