	
first and all eyes. Incidence rates observed in each treatment arm (for first operative eyes, and for all eyes) will be compared to the cumulative and persistent adverse event SPE (safety and performance endpoint) rates based on 1-sided exact binomial calculation.
 
QUVID outcomes will be summarized using standard descriptive measures.
																																										
Sample Size Justification	
Approximately 250 subjects will be bilaterally implanted with either the AcrySof IQ PanOptix IOL Model TFNT00 or the AcrySof Monofocal IOL Model SN60AT in a 1:1 ratio in order to ensure that at least 113 eligible subjects complete the study in the test group and the control group. This assumes a drop-out rate of 10%, approximately.
 
Power calculations for the effectiveness objectives are summarized in the table below:
 

	Margin	Expected Difference	Std. dev	Type I error (1-sided)	Power	

Non- Inferiority						

BCDVA (4 m)	0.1	0.0	0.18	5%	99%	

Superiority						

DCNVA (40 cm)		0.1	0.18	2.5%	98%	

DCIVA (66 cm)		0.1	0.18	2.5%	98%	

Spectacle Wear		20%		2.5%	83%	

 
All expected differences for tests of superiority favor the test lens. Estimates of VA endpoints reported in logMAR.
 
Adverse Events: For any event where a 0 incidence is observed in 113 first-operative eyes in the AcrySof IQ PanOptix IOL test group, the upper exact binomial 95% confidence limit is less than 3%. Thus, with 95% confidence, the true adverse event rate is less than 3%.
 		Margin	Expected Difference	Std. dev	Type I error (1-sided)	Power	Non- Inferiority						BCDVA (4 m)	0.1	0.0	0.18	5%	99%	Superiority						DCNVA (40 cm)		0.1	0.18	2.5%	98%	DCIVA (66 cm)		0.1	0.18	2.5%	98%	Spectacle Wear		20%		2.5%	83%
	Margin	Expected Difference	Std. dev	Type I error (1-sided)	Power																																						
Non- Inferiority																																											
BCDVA (4 m)	0.1	0.0	0.18	5%	99%																																						
Superiority																																											

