4.3.1 Primary Effectiveness Analyses

Least Squares Means (LSMEANS) from the mixed effects model chosen during the model selection step will be employed to estimate the difference in means (AcrySof IQ PanOptix IOL Model TFNT00 minus AcrySof Monofocal IOL Model SN60AT) and the associated 90% (two-sided) confidence interval for the non-inferiority test and 95% (two-sided) confidence interval for the superiority test.

The non-inferiority hypothesis (first co-primary) will be deemed supported if the upper 95% confidence limit is less than the non-inferiority margin of 0.10 logMAR.

The superiority hypothesis (second co-primary) will be deemed supported if the upper 97.5% confidence limit is less than 0.0 logMAR.

SAS pseudo code for the above models is provided below.

```
proc mixed data=visual_acuity;
  where OPERATIVE_EYE = 'First' AND VISIT='VISIT4A';
  class LENS_MODEL SITE;
  model VA = LENS_MODEL /DDFM = satterth;
  random SITE SITE*LENS_MODEL; *[OR] random SITE;
  lsmeans LENS_MODEL / pdiff cl;
  estimate 'Trt_Eff' LENS_MODEL 1 -1;
run;
```

An analysis with a mixed-effect model analysis of variance (ANOVA) accounting for correlation between the first and the second eye will be performed as a sensitivity analyses. The following SAS pseudo code will be used:

```
proc mixed data=visual_acuity;
  where VISIT='VISIT4A';
  class LENS_MODEL SITE OPERATIVE_EYE;
  model VA = LENS_MODEL /DDFM = satterth;
  random SITE SITE*LENS_MODEL; *[OR] random SITE;
  repeated OPERATIVE_EYE / subject=USUBJID(SITE) TYPE=CS;
  lsmeans LENS_MODEL / pdiff cl;
  estimate 'Trt_Eff' LENS_MODEL 1 -1;
run;
```

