5.3.4 Adverse Events

The third safety endpoint is adverse events. Incidence rates observed for each IOL group will be compared to the cumulative and persistent adverse event Safety and Performance Endpoint rates in IS EN ISO 11979-7:2014. An eye with multiple ocular adverse events of the same preferred term is only counted once toward the total of this preferred term. The Safety and Performance Endpoint rate is considered not exceeded if the lower exact binomial 95% confidence limit does not exceed the Safety and Performance Endpoint rate.

The following SAS pseudo code will be used to generate the summaries above.

```
proc freq data=AE_SPE;
by SPE_AE;
tables LENS_MODEL / binomial (exact) alpha=0.05;
run;
```

The frequencies of adverse events will be presented overall, and by subcategories of age (<65 years vs. \geq 65 years) and investigative site, separately for cumulative and persistent adverse events. Additionally, frequencies and 95% (two-sided) exact confidence intervals will be reported for adverse events related to the IOL for each IOL group. Adverse events related to the IOL are referred to as adverse device effects.

Adverse events will be summarized in the following tables, by IOL group:

1. All Adverse Events (Serious and Non-Serious Combined)
 - a. Ocular
 - b. Non-Ocular
2. All Adverse Device Effects
 - a. Ocular
 - b. Non-Ocular
3. All Serious Adverse Events (including Serious Adverse Device Effects)
 - a. Ocular
 - b. Non-Ocular
4. Subject Listings
 - a. Non-Serious Ocular
 - b. Non-Serious Non-Ocular
 - c. Serious Ocular
 - d. Serious Non-Ocular

All ocular tables will be presented separately for first operative eyes and all eyes.

In addition, listings of adverse events will be provided. The listings will include the following variables: treatment, site, subject, eye, days from surgery, duration, adverse event description, causality, severity, seriousness, outcome and preferred term.

Table 5-2**Adverse Event Safety and Performance Endpoint Rates**

Adverse Event	SPE Rate (%)
Cumulative	
Cystoid Macular Oedema	3.0
Hypopyon	0.3

Endophthalmitis ^a	0.1
Lens dislocated from posterior chamber	0.1
Pupillary block	0.1
Retinal detachment	0.3
Secondary surgical intervention ^b	0.8
Persistent	
Corneal stroma oedema	0.3
Cystoid macular oedema	0.5
Iritis	0.3
Raised IOP requiring treatment	0.4

^a Endophthalmitis is defined as inflammatory reaction (sterile or infectious) involving the vitreous body.

^b Excludes posterior capsulotomies.

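### All-eyes SSI intervals and the protocol's all-eyes SPE comparison treat a subject's two eyes as independent; first-eye objectives are unaffected

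*SAP*

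**What the plan says.** **SSI.** SAP 5.3.1 states: "Descriptive summaries (count, rate and 95% (two-sided) exact confidence interval) of secondary surgical interventions will be presented for each IOL group". The same summary covers the difference between lenses and is given "separately for first operative eyes and all eyes in each of the following categories". Protocol 15.7.1.1 has the same plan. The SAP code is PROC FREQ with "exact riskdiff" and no subject term.

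**SPE comparison.** The protocol synopsis states: "Incidence rates observed in each treatment arm (for first operative eyes, and for all eyes) will be compared to the cumulative and persistent". The comparators are the ISO SPE rates, and the method named there is a one-sided exact binomial one. SAP 5.3.4 counts by eye, uses exact binomial limits at alpha=0.05 without a subject term, and adds: "All ocular tables will be presented separately for first operative eyes and all eyes".

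**Scope of the third safety endpoint.** The documents differ. The protocol synopsis (Planned Analyses) and protocol 8.4.2 include all eyes. Protocol 8.3 and SAP 5.1 name first operative eyes only. Protocol 15.7.3 does not say which eyes.

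**Correlation elsewhere.** SAP 4.3.1 has a visual acuity sensitivity analysis "accounting for correlation between the first and the second eye", with a compound-symmetry structure within subject. Neither document gives a clustered or per-subject method for the all-eyes safety rates.

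**The concern.** An exact binomial interval assumes independent units. Each subject chooses one lens model for both eyes, so nearly every subject adds two eyes with the same lens, usually the same surgeon, and the same healing response. If events tend to occur in both eyes of a subject, 250 eyes carry less information than 250 independent observations.

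What is at stake is the accuracy of the planned all-eyes outputs: the SSI interval for each lens, the interval for the difference between lenses, and the error rate of any all-eyes SPE comparison. A reader of the study report would take the printed 95% at face value.

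**Working it through.** **Inputs.** Planned subjects per arm: 125 (250 eyes). Required completers: 113 (226 eyes). Both are from the sample size sections. SPE rates from SAP Table 5-2: 3.0% for cumulative cystoid macular oedema, 0.8% for SSI, and 0.1% to 0.5% for the rest. Rho is not in the documents; 0.3, 0.5 and 0.8 are assumptions, with 0 for reference.

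**The plan's own figure.** For 0 events in 113 first eyes, the plan states an upper 95% limit below 3%. The one-sided limit is 1 − 0.05^(1/113) = 2.62%, which agrees. The two-sided limit is 1 − 0.025^(1/113) = 3.21%, so the statement rests on a one-sided limit.

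**Standard error.** With two eyes per subject the design effect is 1 + rho. Effective n = 250/(1 + rho), and the standard error is understated by 1 − 1/√(1 + rho).

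| rho | effective n | SE understated by |
|---|---|---|
| 0 | 250 | 0% |
| 0.3 | 192 | 12% |
| 0.5 | 167 | 18% |
| 0.8 | 139 | 25% |

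For example, at a 3% rate the independent-eye standard error is √(0.03 × 0.97/250) = 1.08 percentage points. At rho 0.5 it is 1.08 × √1.5 = 1.32 points.

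**Coverage and false flags.** For true rate p:
- P(both eyes) = p² + rho·p(1 − p)
- P(exactly one eye) = 2[p − P(both eyes)]
- P(neither) = the remainder

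At p = 3% and rho 0.5 these are 0.01545, 0.0291 and 0.95545. Convolving 125 such pairs gives the exact distribution of the number of affected eyes. Applying the Clopper-Pearson interval on 250 eyes to each possible count gives:

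| 250 eyes | rho 0 | 0.3 | 0.5 | 0.8 |
|---|---|---|---|---|
| Coverage of 95% interval, p = 3% | 96.1% | 93.0% | 90.7% | 86.9% |
| Upper limit below the true rate, p = 3% (nominal 2.5%) | 1.9% | 3.4% | 4.7% | 7.1% |
| Coverage of 95% interval, p = 0.8% | 98.4% | 96.9% | 96.0% | 94.4% |
| 3.0% SPE wrongly exceeded, protocol 1-sided 95% limit | 4.0% | 6.2% | 7.5% | 9.2% |
| 3.0% SPE wrongly exceeded, SAP code (two-sided limits) | 2.0% | 3.6% | 4.6% | 6.0% |

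The last two rows take the true rate as exactly 3.0%. With 226 eyes, coverage at 3% is 97.2% / 94.7% / 92.8% / 90.2%, and at 0.8% it is 99.0% / 97.8% / 97.1% / 95.7%.

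**Illustration.** For 6 events in 226 eyes (2.65%), the planned interval is 0.98% to 5.69%. With effective n 151 (rho 0.5) it is 0.73% to 6.66%. With effective n 113 (rho 1) it is 0.55% to 7.56%.

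**The case against.** The strongest reply is that nothing decisive rests on these outputs. The co-primary SSI objective and the third safety objective are stated for first operative eyes, SAP 5.2 describes the safety assessment as mainly descriptive, and valid first-eye results will stand beside the all-eyes ones. This stands. It limits the importance of the point but does not make the all-eyes intervals correct.

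Four stronger readings are tempting, and the documents do not support them:

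- **All-eyes SSI intervals in general miss 95% coverage.** At the 0.8% SSI rate they stay close to nominal, because exact intervals are conservative for rare events. Ten of the eleven SPE rates are 0.8% or lower. The shortfall is clear at about 3%.
- **Each arm holds only 125 independent units.** That is true only at rho 1. At the assumed values, effective n is 139 to 192.
- **The error makes the test lens look safer.** The SPE rule uses the lower limit, so correlation adds false findings of an exceeded rate, which count against the lens. The upper limit that is too low at rates near 3% and above counts in its favour. At a true 0.8% the upper limit cannot fall below the truth: even zero events in 250 eyes gives 1 − 0.025^(1/250) = 1.46%.
- **The SAP firmly plans an all-eyes SPE comparison.** The protocol synopsis does. In SAP 5.3.4 the all-eyes sentence follows the list of general adverse event tables, and SAP 5.1 names first eyes only.

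A practical objection also stands. At 0.8%, 250 × 0.008 = 2 events are expected per arm. Rho cannot be estimated from so few, and GEE or a subject-level bootstrap would be unstable.

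**Conclusion.** The concern holds for the all-eyes summaries only. The planned all-eyes SSI intervals, the interval for the difference between lenses, and the protocol's all-eyes SPE comparison use independent-eye formulas for paired eyes, although the SAP models between-eye correlation for visual acuity.

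The size depends on rho, which is assumed. Over 0.3 to 0.8 with 250 eyes per arm, coverage falls to between 93% and 87% at a 3% rate, but stays between 97% and 94% at 0.8%. The chance of wrongly flagging the 3.0% event rises from 4% to between 6% and 9% under the protocol's one-sided limit, or from 2% to between 4% and 6% under the SAP code. At rho 0 there is no error. The change should be made because it is cheap and the outputs are pre-specified, but no effectiveness conclusion or first-eye safety objective depends on it.

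**What to change.** In SAP 5.3.1 and 5.3.4:

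1. Keep exact intervals for first eyes, and give second eyes their own exact intervals. The SAP already separates first and second eyes for IOP, slit lamp and posterior capsule opacification (5.3.5, 5.3.6, 5.3.12).
2. Show all-eyes results as counts and percentages only, or as the proportion of subjects with at least one affected eye, with an exact interval on subjects.
3. If an all-eyes interval is kept, use a conservative exact interval with effective n equal to the number of subjects. This needs no estimate of rho.
4. Limit the exact SPE comparison to first eyes. Reconcile the protocol synopsis and protocol 8.4.2, which include all eyes, with SAP 5.1, which does not. State at the same time whether the SPE limit is one-sided 95% (synopsis) or the lower end of a two-sided 95% interval (SAP code).

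The cost is SAP wording and a few lines of code, with no new data and no change to a primary analysis. The downside is that all-eyes intervals become wider or are dropped. The per-subject rate also answers a different question from the per-eye rate and must be labelled so.

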1.1 Study Objectives

Effectiveness Objectives

The co-primary effectiveness objectives are to:

- Demonstrate non-inferiority of AcrySof IQ PanOptix IOL Model TFNT00 compared to the concurrent control AcrySof Monofocal IOL Model SN60AT in mean photopic monocular best corrected distance visual acuity (4 m) for the first operative eye at month 6 (Visit 4A).
- Demonstrate superiority of AcrySof IQ PanOptix IOL Model TFNT00 compared to the concurrent control AcrySof Monofocal IOL Model SN60AT in mean photopic monocular distance corrected visual acuity at near (40 cm) for the first operative eye at month 6 (Visit 4A).

The secondary effectiveness objectives are to:

- First secondary: Demonstrate superiority of AcrySof IQ PanOptix IOL Model TFNT00 compared to the concurrent control AcrySof Monofocal IOL Model SN60AT in mean photopic monocular distance corrected visual acuity at intermediate (66 cm) for the first operative eye at month 6 (Visit 4A).
- Second secondary: Demonstrate superiority of AcrySof IQ PanOptix IOL Model TFNT00 compared to the concurrent control AcrySof Monofocal IOL Model SN60AT in proportion of subjects who respond “Never” to Q1 of the IOLSAT questionnaire (Overall, in the past 7 days, how often did you need to wear eyeglasses to see?) at month 6 (Visit 4A).

Safety Objectives

The co-primary safety objectives are to:

- Estimate the cumulative rate of secondary surgical interventions (SSIs) related to the optical properties of the IOL for first operative eye up to month 6 (Visit 4A).
- Evaluate the mean binocular contrast sensitivity with and without glare for photopic and mesopic conditions at month 6 (Visit 4A).

The secondary safety objective is to:

- Estimate rates of severe and most bothersome (separately) visual disturbances as reported by the subjects using a questionnaire (QUVID) at month 6 (Visit 4A).

The third safety objective is to:

- Evaluate rates of cumulative and persistent Adverse Events in first eyes at 6 months (Visit 4A) in comparison to IS EN ISO 11979-7:2014 Safety and Performance Endpoint grid rates.

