1.2 Study Description

This study is a prospective, multi-center, non-randomized, vision assessor-masked, parallel group confirmatory trial. It compares an investigational trifocal IOL and a commercially available monofocal IOL. Approximately 125 subjects will be implanted bilaterally with the investigational lens and approximately 125 subjects will be implanted bilaterally with the control lens. Potential subjects will be screened for enrollment into the trial. Those qualifying will attend a total of 10 visits (7 visits occur postoperatively) over a 7 month period.

An overview of the study design is depicted in Table 1-1.

The schedule of visits is presented in Section 6 of the protocol.

Table 1-1 **Study Design**

Time From Implantation	1st Eye	2nd Eye
-30 to 0 days pre-operatively	Visit 0 (monocular [1st and 2nd eye] and binocular)	
Operative (IOL implantation)	Visit 00	Visit 00A*
1 - 2 days post-operatively	Visit 1 (monocular)	Visit 1A (monocular)
7 - 14 days post-operatively	Visit 2 (monocular)	Visit 2A (monocular)
30 - 60 days post-operatively	Visit 3 (monocular)	Visit 3A (monocular)
120 - 180 days post-operatively (after 2nd eye implantation)	Visit 4A** (monocular [1st and 2nd eye] and binocular)	

*NOTE: IOL implantation in the second eye is intended to occur between 7 and 30 days after IOL implantation in the first eye.

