5.3.3 Visual Disturbances

The secondary safety endpoint is rates of severe and most bothersome visual disturbances as reported by subjects using the QUVID questionnaire at month 6. Descriptive summaries (rates and 95% (two-sided) exact confidence intervals) of severe and most bothersome visual disturbances will be presented for each IOL group and the difference between the IOL groups.

The number and percentages of subjects in each category of responses to each question on the QUVID questionnaire will be reported by IOL group at each visit this questionnaire is administered.

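### SAP 5.3.1 and 5.3.3 promise exact between-lens intervals for SSIs and visual disturbances without naming the statistic; for rare SSIs the choice changes the width more than threefold.

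*SAP*

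**What the plan says.** The SSI objective in SAP 1.1 is to estimate the cumulative rate of SSIs "related to the optical properties of the IOL for first operative eye up to month 6 (Visit 4A"). It is one of two co-primary safety objectives.

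For the analysis, SAP 5.3.1 plans a count, a rate and a two-sided 95% "exact confidence interval) of secondary surgical interventions will be presented for each IOL group and the difference between the groups". Protocol 15.7.1.1 plans the same. The only further specification is the SAP's pseudo code: a table request, "tables LENS_MODEL*SSI / alpha=0.05", followed by "exact riskdiff". No statistic or method option is given, and the text does not say which lens is subtracted from which.

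For QUVID, the secondary safety endpoint, SAP 5.3.3 plans rates and two-sided 95% "exact confidence intervals) of severe and most bothersome visual disturbances will be presented for each IOL group and the difference between the IOL groups", without code. Protocol 15.7.2 is equally general.

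SAP 5.2 describes the safety analysis as descriptive. Neither document sets a margin, hypothesis or target precision for either difference, or gives an expected rate of optical-property SSIs.

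**The concern.** For a single proportion, an exact interval in the usual Clopper-Pearson sense is fully defined. For a difference of two proportions it is not. The tail probability has to be maximised over an unknown nuisance rate, and the answer depends on how the possible tables are ordered.

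- If tables are ordered by the unstandardised difference, the worst case is a rate near 50%, where the variance is largest. The interval is then about as wide for a 1% event as for a 50% event.
- If tables are ordered by the score statistic, which divides the difference by its standard error under the hypothesised difference, coverage is still at least 95% but the width follows the observed rates.

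Both satisfy the word exact in the SAP, and both are admissible readings of its code. SSIs are expected to be rare, which is where the two differ most. At stake is the only planned interval that compares the lenses on this endpoint. Leaving the choice open also means it could be made after the data are seen.

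**Working it through.** **Inputs.**
- Arm sizes, SAP 1.2: "Approximately 125 subjects will be implanted bilaterally with the investigational lens" and "approximately 125 subjects will be implanted bilaterally with the control lens". SSIs are analysed in the Safety Analysis Set, which keeps all attempted eyes, so about 125 first eyes per arm is the natural figure. The completer target in SAP 7, 113 per arm, is the lower case.
- Level: two-sided 95% (SAP 5.3.1).
- Event rate: none is given for optical-property SSIs. The nearest figure is the Safety and Performance Endpoint (SPE) rate of 0.8% for all SSIs excluding capsulotomy (SAP Table 5-2), or 0.008 × 125 = 1 event per arm. The event counts below are scenarios.

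**The plan's own precision figure.** SAP 7 states that with 0 events in 113 eyes the upper exact 95% limit is below 3%. This reproduces as a one-sided limit: 1 - 0.05^(1/113) = 2.62%. The two-sided counterpart is 1 - 0.025^(1/113) = 3.21%. No precision is stated for the difference.

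**Method.** For each candidate difference d, compute the probability of a table at least as extreme as the one observed, maximise it over the nuisance rate, and keep d if the maximum exceeds 2.5% in each tail. This was done once ordering tables by the raw difference and once by the restricted-maximum-likelihood score statistic.

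**Results**, in percentage points, test minus control:

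| n per arm | Events (test v control) | Unstandardised exact | Score-based exact |
|---|---|---|---|
| 125 | 0 v 0 | -12.7 to +12.7 | -3.2 to +3.2 |
| 125 | 1 v 0 | -11.9 to +13.5 | -2.4 to +4.5 |
| 125 | 1 v 1 | -12.7 to +12.7 | -3.8 to +3.8 |
| 125 | 2 v 2 | -12.7 to +12.7 | -4.3 to +4.3 |
| 125 | 6 v 0 | -8.0 to +17.5 | +1.3 to +10.3 |
| 113 | 0 v 0 | -13.4 to +13.4 | -3.4 to +3.4 |
| 113 | 1 v 1 | -13.4 to +13.4 | -4.1 to +4.1 |

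**Hand checks.** For the unstandardised version, the largest variance of the difference at d = 0.127 is (0.5 - d²/2)/125 = 0.4919/125 = 0.003936. Then 1.96 × √0.003936 = 12.3 points, and half a lattice step, 1/(2 × 125) = 0.4 points, brings it to 12.7. For the score version at 0 v 0, the large-sample limit solves d² = 3.8416 × d(1 - d)/125, so d = 3.8416/(125 + 3.8416) = 2.98 points. The exact version adds a little, giving 3.15.

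**Ratio of widths.** At 1 v 1 it is 12.73/3.76 = 3.4, at 2 v 2 it is 12.73/4.28 = 3.0, and with no events it is 12.73/3.15 = 4.0.

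**Where zero is first excluded with no control events.** The score version excludes it at 4 v 0 (lower limit +0.02). The unstandardised version excludes it at 16 v 0 (lower limit +0.02), and still spans zero at 15 v 0 (-0.8 to +24.5).

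**QUVID illustration.** No expected rates are given. With 12 v 3 of 113, the unstandardised interval is -5.5 to +21.2 and the score-based interval is +1.5 to +15.5.

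**The case against.** The strongest reply is that little depends on this interval, and much of that stands.

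- **No rule uses it.** The objective is to estimate, and no margin or test applies to the difference. Counting when an interval first excludes zero applies a test that the plan does not make. A wide interval is still valid, and it alters neither the point estimate nor the per-lens rates.
- **Other outputs would show an excess.** A reader might infer that the unstandardised interval would hide a clear excess of SSIs with the test lens, or leave the comparison uninformative. The documents do not support that. SAP 5.3.1 also requires counts, an exact interval for each lens and a listing of every SSI. At 6 v 0 the reader would see 6/125 with limits 1.8% to 10.2% beside 0/125 with limits 0% to 2.9%. SAP 5.3.4 compares each lens with the 0.8% SPE rate and treats it as exceeded when the lower exact limit lies above it. For 4/125 the two-sided lower limit is 0.88%, so that rule flags the test lens at 4 events, the same count at which the score-based difference interval first excludes zero.
- **The default is unknown.** A reader might infer that the code will certainly produce the wide version. The documents do not give the software default, and a release that applies the score version would need no change in practice.
- **It is pseudo code.** The final program may name a method, and 5.3.3 gives no code at all, so the QUVID figures only illustrate the range.

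What survives is narrower. Neither document names the statistic in text or code, and the admissible choices differ more than threefold in width on the plan's only between-lens interval for this endpoint. That the comparison is descriptive makes this less serious, but does not justify leaving the interval undefined.

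**Conclusion.** The point holds as an underspecified interval with a better option available at almost no cost. At 125 per arm and low SSI counts, the half-width is about 12.7 points under one reading and 3.2 to 4.3 under the other for the equal counts of 0 to 2 per arm tabulated. The ±3.2 applies only when neither arm has an event. At one event per arm, a rate of 0.8%, the figure is ±3.8.

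The result assumes about 125 first eyes per arm (at 113 the contrast is similar) and low SSI counts, for which the only anchor in the documents is the SPE rate. It does not depend on which version the software applies by default. No success criterion is affected. The gain is a between-lens interval whose width reflects the rarity of the event, with the method fixed in advance. This is a change that should be made, not a flaw that undermines the safety evaluation.

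**What to change.** In SAP 5.3.1, name the score-based exact unconditional interval in the text and write the code as `exact riskdiff(method=score)`, checking the syntax against the software release to be used. State that the difference is TFNT00 minus SN60AT in the proportion with SSI = Yes. In SAP 5.3.3, name the same score-based exact interval for the differences in severe and most bothersome visual disturbances. Make both changes before the data are analysed.

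The cost is one code option and a line of text in each section. No extra data are needed, coverage stays at or above 95%, and nothing changes if the score version was already intended.
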